8.5. External Data

External Data are subject data obtained externally to the CRF. These data are generated from laboratory instruments, computers or other sources and then transcribed into a file and format agreed upon by GSKCH to identify the subject and time point referenced in the CRF and/or protocol.

An agreed upon quality control process is performed against the transcribed data to the source to ensure the accuracy of the transcription. The transcribed data is transmitted in an agreed upon format to GSKCH via secured web portal or CD/DVD via mail carrier with tracking capabilities.

Proper reconciliation will be performed between the transcribed data and the clinical database to ensure subject and time point referenced in the Clinical Database match before Clinical Database Freeze (locking of the database) can occur.

9. STATISTICAL CONSIDERATIONS AND DATA ANALYSES

9.1 Sample Size Determination

The primary efficacy variable of the study is the total number of ill days due to GI and respiratory illnesses. The sample size has been calculated based on the assumption of an average of 7 ill days in the control group with a difference of 10% between the treatments.

 GlaxoSmithKline	Document Name	Clinical Study Protocol 204477		
	Type	Version	Document Identifier	Effective Date
	eldo_clinical_doc	5.0; Most-Recent; Effective; CURRENT	090032d580daa95e	10-Oct-2017 06:16:49
	Reason For Issue	Auto Issue		

Years Lost due to Disability (YLD) is a measure of the burden of disease from its morbidity. Below are data that are specific to India: As per the data from Global Burden Disease, WHO 2010 study (GBD, WHO, 2012; IHME, 2013) and Census India, 2011, YLD per child in the 5-9 year age group, due to diarrhea, LRTIs, other infectious disease and nutritional deficiencies is 8.274 days/child per year or 6.21 days/child per 9 months.

Thus, based on above data, approximately 7 ill days due to GI and respiratory illnesses per 9 months has been assumed in this proposed study population of 7-10 year olds.

The sample size is based on the primary endpoint. No sample size considerations have been taken into account for secondary objectives.

The simulated data were also used based upon the assumption of a Poisson distribution per study treatment. On observation of these simulated data, it was considered that these Poisson distributions were not heavily skewed and, as a result, normal distributions may be assumed. Consequently, a normality assumption has been adopted for both the generation of sample size and the intended approach to the statistical analysis.

Because of assumption of poisson distribution, estimates of variability were calculated as square root of mean.

Mean of control was assumed to be 7.0 and standard deviation (SD) was 2.65, mean of test group was 6.3 and SD was 2.51. To be able to achieve 80% power, 215 participants per treatment arm (Total = 430) will be required to complete the study in case of individual randomisation. This assumes 5% level of significance (two tailed t-test).

As this study is using cluster randomisation, and design effect (DE) needs to be considered for sample size calculations. Scientific literature suggests, DE due to cluster sampling strategy can be assumed to be 1.5 [Rosner, B, 1986]. Same has been assumed in one study, which used three-stage systematic cluster sampling [Dandona R *et al*, 2008].

Using the following formula from Hemming *et al*, 2011:

$$N^* = N \times DE$$

Where N*=Number of participants required for cluster randomised trial

 GlaxoSmithKline	Document Name	Clinical Study Protocol 204477		
	Type	Version	Document Identifier	Effective Date
	eldo_clinical_doc	5.0; Most-Recent; Effective; CURRENT	090032d580daa95e	10-Oct-2017 06:16:49
	Reason For Issue	Auto Issue		

N = Number of participants required for individual randomisation

DE = Design Effect

And assuming DE to be 1.5, the number of evaluable participants completing the study required would be 323 per arm (Total=646).

To allow for 30% drop-out rate, a total of 924 participants will be randomised.

Approximately 1300 participants will be screened to randomise approximately 924 participants in order to obtain 646 participants completing the study.

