6.11.2. Morbidity Outcomes Definitions

Following morbidity outcomes with respect to GI and respiratory illnesses are going to be evaluated in the study:

- A. **Number of illness days:** Number of days a participant is ill because of GI and/or respiratory illnesses as diagnosed by study physician, as per the criteria defined, over the intervention duration. This corresponds to total number of days (symptomatic or asymptomatic) in an episode of illness.
- B. **Frequency of illnesses:** Total number of illness episodes of GI and/or respiratory illnesses, divided by duration of intervention, where each episode is defined as each incidence of illness followed by at least 3 symptom free days [Azor-Martínez *et al.*, 2014] [Barreto ML *et al.*, 1994] [Sur D *et al.*, 2003].

For the purpose of study, each occurrence of an illness is defined as an event which incorporates a period which includes all illness days uninterrupted by any symptom free day. Thus, an episode may consist of one or more than one occurrences of illness.

- C. **Severity of an illness episode:** Intensity of GI and/or respiratory illnesses; **WILL BE EVALUATED AND CLASSIFIED AS PER CRITERIA SPECIFIED IN APPENDIX-5 (BASED ON CTCAE 2010)** ~~which is evaluated and classified as follows:~~

- ~~➤ Severity of GI illnesses [CTCAE 2010]~~
- ~~a. Diarrhoea:~~

 GlaxoSmithKline	Document Name	Clinical Study Protocol 204477		
	Type	Version	Document Identifier	Effective Date
	eldo_clinical_doc	5.0; Most-Recent; Effective; CURRENT	090032d580daa95e	10-Oct-2017 06:16:49
	Reason For Issue	Auto Issue		

- ~~Mild, ≤ 3 loose stools/day~~
- ~~Moderate, 4 to 6 loose stools/day~~
- ~~Severe, ≥ 7 loose stools/day~~

~~b. Vomiting:-~~

- ~~Mild, 1 to 2 bouts/day~~
- ~~Moderate, 3 to 5 bouts/day~~
- ~~Severe, ≥ 6 bouts/day~~

~~➤ Severity of respiratory illnesses~~

- ~~Mild Easily tolerated, causing minimal discomfort and not interfering with normal everyday activities.~~
- ~~Moderate Sufficiently discomforting to interfere with normal everyday activities.~~
- ~~Severe Any event that prevents normal everyday activities.~~

D. School absenteeism: Number of days when a child fails to attend school because of GI and/or respiratory illnesses.

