9.3.2. Primary Analyses

The primary efficacy variable of the study is the number of ill days. The number of ill days is defined as number of days a subject is ill because of GI and/or respiratory illnesses as diagnosed by study physician, as per the criteria defined in Section 6.11.1 and 6.11.2, over the intervention period.

For this variable, primary analysis will be performed on participants in ITT population who have completed the entire study for 9 months.

The null hypothesis of interest is:

H₀: There is no difference in the number of ill days.

The alternative hypothesis of interest is:

H₁: There is a difference in the number of ill days.

The number of ill days will be summarised in terms of number (N), mean, standard deviation, minimum, and maximum for both the treatment groups.

The number of ill days will be analysed using the analysis of variance (ANOVA). The ANOVA will have treatment, cluster (school), and gender as fixed effects.

Adjusted means, 95% confidence intervals, within treatment p-values for each treatment group, treatment group difference, 95% confidence interval of the difference and the between-treatment p-values based on the statistical model described above will also be presented.

All statistical tests of hypotheses will be two-sided and will employ a level of significance of $\alpha = 0.05$.

The simulated data used for the sample size calculations were based upon the assumption of a Poisson distribution per study treatment. However, on observation of these simulated data, it was considered that these Poisson distributions were not heavily skewed and, as a result, normal distributions may be assumed. Consequently, a normality assumption has been adopted for both the generation of sample size and the intended approach to the statistical analysis. However, the assumptions of normality and homogeneity of variance will be investigated and violation of these assumptions may be overcome using suitable transformation (for example, log or square root). If transformed data is also non-normal, then alternative analyses relevant to Poisson distributed data will be investigated (further details will be

 GlaxoSmithKline	Document Name	Clinical Study Protocol 204477		
	Type	Version	Document Identifier	Effective Date
	eldo_clinical_doc	5.0; Most-Recent; Effective; CURRENT	090032d580daa95e	10-Oct-2017 06:16:49
	Reason For Issue	Auto Issue		

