1.4 Sample Size Calculation

The primary efficacy variable of the study is the total number of ill days due to GI and respiratory illnesses. The sample size has been calculated based on the assumption of an average of 7 ill days in the control group with a difference of 10% between the treatments.

Years Lost due to Disability (YLD) is a measure of the burden of disease from its morbidity. Below are data that are specific to India: As per the data from Global Burden Disease, WHO 2010 study (GBD, WHO, 2012; IHME, 2013) and Census India, 2011, YLD per child in the 5-9-year age group, due to diarrhea, LRTIs, other infectious disease and nutritional deficiencies is 8.274 days/child per year or 6.21 days/child per 9 months.

Thus, based on above data, approximately 7 ill days due to GI and respiratory illnesses per 9 months has been assumed in this proposed study population of 7-10 year olds.

The sample size is based on the primary endpoint. No sample size considerations have been taken into account for secondary objectives.

The simulated data were also used based upon the assumption of a Poisson distribution per study treatment. On observation of these simulated data, it was considered that these Poisson distributions were not heavily skewed and, as a result, normal distributions may be

assumed. Consequently, a normality assumption has been adopted for both the generation of sample size and the intended approach to the statistical analysis.

Because of assumption of Poisson distribution, estimates of variability were calculated as square root of mean.

Mean of control was assumed to be 7.0 and standard deviation (SD) was 2.65, mean of test group was 6.3 and SD was 2.51. To be able to achieve 80% power, 215 participants per treatment arm (Total = 430) will be required to complete the study in case of individual randomisation. This assumes 5% level of significance (two tailed t-test).

As this study is using cluster randomization, and design effect (DE) needs to be considered for sample size calculations. Scientific literature suggests, DE due to cluster sampling strategy can be assumed to be 1.5 [Rosner, B, 1986]. Same has been assumed in one study, which used three-stage systematic cluster sampling [Dandona R *et al*, 2008].

Using the following formula from Hemming *et al*, 2011:

$$N^* = N \times DE$$

Where N^* = Number of participants required for cluster randomized trial

N = Number of participants required for individual randomization

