4.4 Analysis of Efficacy

4.4.1 Primary Efficacy Endpoint

4.4.1.1 Primary Efficacy Endpoint Definition

The primary efficacy variable of the study is the number of ill days over a period of nine months.

The definition of number of illness days is following –

Number of illness days: Number of days a subject is ill because of GI and/or respiratory illnesses as diagnosed by study physician, as per the criteria defined, over the intervention duration. This corresponds to total number of days (symptomatic or asymptomatic) in an episode of illness. Each episode is defined as each incidence of illness followed by at least 3 symptom free days.

In an episode if the first occurrence is due to GI illness and second occurrence is due to respiratory illness with less than 3 symptom free days then the overall episode due to GI and/or respiratory will be counted as one and separately it will be one each for GI and respiratory.

The asymptomatic days (or symptom free) days will be calculated programmatically based on the date mentioned on the Diagnosis Form in the following way –

Asymptomatic day = (Second occurrence start date - First occurrence end date) - 1

If asymptomatic day is less than 3 days then two occurrences of illnesses will be calculated and considered as single episode.

Else if asymptomatic days are greater than or equal to 3 days then two occurrences of illnesses will be calculated and considered as different episodes.

Descriptive statistics (n, mean, SD, SE, median, minimum and maximum) by product group will be provided ([Table 14.2.2.1](#)). Number of ill days due to GI and/or respiratory illnesses will be listed for each subject ([Listing 16.2.6.18](#)).

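### The sample size sets the SD at the square root of the mean, but ill days are summed over multi-day episodes, so the stated 80% power at a mean of 7 is unsupported once episodes last more than about a day

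*Protocol*

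**What the plan says.** Protocol 9.1 treats the number of ill days over nine months as Poisson: "Because of assumption of poisson distribution, estimates of variability were calculated as square root of mean". SAP 1.4 carries the resulting inputs: "Mean of control was assumed to be 7.0 and standard deviation (SD) was 2.65, mean of test group was 6.3 and SD was 2.51". A two-sided 5% t-test with 80% power then needs 215 per arm. A design effect of 1.5 for cluster sampling raises this to 323 evaluable per arm, and a 30% loss allowance gives 924 enrolled.

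The support offered for the distribution is a set of simulated Poisson data, on which the protocol concludes that "these Poisson distributions were not heavily skewed and, as a result, normal distributions may be assumed".

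The endpoint itself is defined in Protocol 6.11.2: "This corresponds to total number of days (symptomatic or asymptomatic) in an episode of illness". SAP 4.4.1.1 adds "Each episode is defined as each incidence of illness followed by at least 3 symptom free days" and the joining rule "If asymptomatic day is less than 3 days then two occurrences of illnesses will be calculated and considered as single episode". An episode can therefore hold several occurrences, with symptom-free gaps of up to two days counted as ill days. Occurrences are recorded by start and end date on the Diagnosis Form (Protocol Appendix 5).

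**The concern.** A Poisson model could suit the number of episodes, which is the basis of a separate secondary endpoint. It does not suit the total of days within them. If one illness contributes three consecutive days, those days are not independent events, and the child-to-child variance of the total is larger than its mean. Differences between children in how often they fall ill add further variance.

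Nothing else in the plan supplies this variance. The design effect of 1.5 is for schools only. The simulated data were Poisson by construction, so they could show skewness but could not test whether variance equals the mean. At the analysis stage, Protocol 9.3.2 says that "the assumptions of normality and homogeneity of variance will be investigated and violation of these assumptions may be overcome using suitable transformation", and SAP 4.4.1.2 adds Poisson regression and rank methods, but neither alters the SD behind the 80% claim. No interim analysis is planned and no sample-size re-estimation is described.

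Protocol 9.2.3 makes success a statistically significant decrease in ill days. If real power is nearer 40% than 80%, a null result could be read as evidence of no benefit when the trial was unlikely to detect the planned 10% difference.

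**Working it through.** **Inputs from the documents.** Means 7.0 and 6.3, difference 0.7; SDs 2.65 and 2.51; two-sided 5%; 80% power; design effect (DE) 1.5; 30% loss (Protocol 9.1, SAP 1.4). At least 3 symptom-free days between episodes (Protocol 6.11.2, SAP 4.4.1.1). Nine months taken as 270 days, as SAP 4.4.2 counts a month as 30 days.

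**Assumed, because the documents do not give them.** Episode length L, and the between-child coefficient of variation (CV) of the episode rate.

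**1. The plan's own figures reproduce.** Pooled SD = √((2.65² + 2.51²)/2) = 2.581. The t-test with 215 per arm has power 80.1%. Then 215 × 1.5 = 322.5, rounded up to 323; 323/0.70 ≈ 462 per arm, or 924.

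**2. Variance without the gap rule.** If the number of episodes is Poisson and an episode lasts D days, variance/mean of total days = E[D²]/E[D]. For a fixed length L this ratio is L; variable lengths make it larger.

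**3. Variance with the gap rule.** Simulation of 500,000 children per arm: fixed length L, next start at least L + 3 days after the last start, then an exponential wait with its rate set to give mean 7.0 or 6.3. The enforced gap makes episodes slightly more regular, so the ratio is below L. For L = 2, 3, 4 and 5 the two arm variances sum to V = 0.88, 0.90, 0.92 and 0.92 times the no-gap value (7.0 + 6.3) × L = 13.3 × L, that is V ≈ 23.4, 35.9, 48.9 and 61.2.

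**4. Power.** Power = Φ(0.7/√(1.5V/323) − 1.96). With the plan's V = 13.3: √(1.5 × 13.3/323) = 0.2485, 0.7/0.2485 = 2.817, power 80%. With L = 3: √(1.5 × 35.9/323) = 0.408, 0.7/0.408 = 1.71, power 40%. If the between-school variance is held fixed instead of DE, 1.5V becomes V + 0.5 × 13.3 = V + 6.65.

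| L (days) | Variance/mean, control | Control SD (plan 2.65) | Power, DE 1.5 | Power, no gap rule | Power, school variance held | Power, CV 0.3, DE 1.5 |
|---|---|---|---|---|---|---|
| 1 | 0.81 | 2.4 | 87% | 80% | – | – |
| 1.2 | 0.99 | 2.6 | 80% | – | – | – |
| 2 | 1.75 | 3.5 | 56% | 51% | 63% | 46% |
| 3 | 2.70 | 4.3 | 40% | 37% | 49% | 35% |
| 4 | 3.65 | 5.1 | 31% | 29% | – | – |
| 5 | 4.59 | 5.7 | 26% | 24% | 33% | 24% |

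(– = not calculated.) A version that steps through whole days gives the same values to within about one percentage point.

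**5. A higher true mean.** The same model at mean 21 with a 10% difference (2.1 days) gives, without between-child variation and with CV 0.3: L = 2, about 99% and 87%; L = 3, about 90% and 74%; L = 5, about 70% and 57%.

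**6. Degrees of freedom.** All figures above use 1.96. SAP 3.3 has four schools, SAP 4.4.1.2 fits school as a random effect, and no degrees-of-freedom method is named. If the treatment test had 2 df (an assumption; critical value 4.303), the plan's own 80% would become about 35%, and L = 2, 3 and 5 would give about 24%, 18% and 13%. That drop comes from the number of schools and is separate from the variance fault.

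**The case against.** The strongest reply is that the size of the shortfall is unknown. No episode length, SD or between-child variation is documented, and across the assumptions above power runs from about 13% to about 99%. One-day episodes even make the plan slightly conservative. This stands as a limit on any single power figure. It does not rescue the claim, because a power statement has to hold at its own inputs. At a mean of 7, the stated 80% holds only if episodes average about a day and children barely differ in illness rate.

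Second, the 2-df figures bring in a different problem, the small number of schools. That is fair. They should not be added to the variance shortfall, and they matter here only because a restated power has to say which degrees of freedom it uses.

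Third, features left out of the calculation could help. Gender and baseline dietary diversity score are in the model and may absorb some between-child variance, and a fallback analysis could have different power. The amounts are unknown. If no child were lost, 462 per arm would give about 72% for 2-day and 54% for 3-day episodes, still short of 80%.

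Fourth, SDs, the intracluster correlation and confidence intervals will be reported, so a reader can judge precision directly, and by SAP Amendment 1 (2 November 2018) a change to Protocol 9.1 would be largely retrospective. Both points limit the consequence, but neither makes the stated 80% correct.

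**Conclusion.** The concern holds. SD = √mean is not justified for an endpoint that counts every day of multi-day episodes, and nothing in either document supplies the missing variance. The direction is firm at the planned mean once episodes exceed about 1.2 days. The size is illustrative: about 56%, 40%, 31% and 26% power for fixed lengths of 2, 3, 4 and 5 days (mean 7, 3-day gap, DE 1.5, normal approximation), lower with between-child variation, and higher if the between-school variance rather than DE is held or if the true mean is well above 7. The fault affects planning and the reading of a null result. It does not affect the validity of the primary test or its interval, which estimate the variance from the data.

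**What to change.** In Protocol 9.1 and SAP 1.4:

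- Withdraw the statement that SD = √mean gives 80% power.
- Replace it with an overdispersed variance: negative binomial, or compound Poisson with a stated episode length, at least 3 symptom-free days between episodes, and between-child variation. State where these values come from, for example diary data on ill days per child, so that one unsupported input does not replace another.
- Restate power at 323 per arm as a short sensitivity table. For each row give the control mean, the episode length, whether the design effect or the between-school variance is held, and the degrees of freedom.
- Add one sentence that the Poisson simulations address skewness only and do not support the variance.

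The cost is text and one table, with no added children and no change to conduct or analysis. The protocol change needs an amendment under the protocol's own process, including IRB/IEC submission as the country requires. The stated power at the planned mean will be less favourable, and more so if few degrees of freedom are acknowledged.

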6.1. Matched Pair Formation

Each school will be deemed as a cluster. Schools with following characteristics will be invited to participate in the study:

- ~~Located in peri-urban areas~~
- No government or sponsored micronutrient supplementation scheme running in past 6 months
- Mixed-gender education/co-education system of education
- No history of any outbreak or clustering of cases of infectious diseases in last month

Schools which agree to participate will be selected and will be subsequently matched for cluster size (in context to the number of children in 7-10 yrs age group), socioeconomic profiles of students, and type of school; government subsidised or private.

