3.3 Centers Pools

This study is conducted in multiple (4) schools, with two schools in each product group.

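### The design effect of 1.5 has no intracluster correlation or school size behind it: with four schools it implies an ICC of 0.0031 that is stated and justified nowhere, and the 80% power claim depends on it

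*Protocol*

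**What the plan says.** Protocol 9.1, repeated in SAP 1.4, starts from an "average of 7 ill days in the control group with a difference of 10% between the treatments" and an individually randomised comparison: "Mean of control was assumed to be 7.0 and standard deviation (SD) was 2.65, mean of test group was 6.3 and SD was 2.51". On those inputs, "To be able to achieve 80% power, 215 participants per treatment arm (Total = 430) will be required". The test is two-sided: "This assumes 5% level of significance (two tailed t-test".

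Clustering enters through one multiplier: "Scientific literature suggests, DE due to cluster sampling strategy can be assumed to be 1.5". The support is a biostatistics textbook and one other paper: "Same has been assumed in one study, which used three-stage systematic cluster sampling". The reference list shows that the second source is about road traffic injuries. The result is 323 completers per arm (646 in all), raised to 924 for 30% dropout.

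On the number of schools, Protocol 3.3 asks for at least four, with at least two per group. The SAP is definite: "This study is conducted in multiple (4) schools, with two schools in each product group". Protocol 3.4 accepts that cluster sampling can reduce the effective sample size and that more clusters would help, then settles on at least two per group for feasibility.

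SAP 4.4.1.2, as changed by Amendment 1, fits school as a random effect in the primary ANCOVA. The amendment describes adjustment for the ICC as necessary for validity. SAP 1.4 still carries the protocol's sample size calculation.

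**The concern.** A design effect is not a constant that can be carried from one study to another. It equals 1 + (m − 1) × ICC, where m is the number of children analysed per cluster. The same 1.5 stands for very different correlations with 20 children per school and with 160. Neither cited source is put forward as a school-randomised trial or as evidence on infectious illness, and the plan never converts the 1.5 into an ICC that a reader could judge.

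Both the 323 per arm and the 80% power rest on this number. With few, large schools, power is very sensitive to it. A null result would be read against an 80% claim that the documents do not support.

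**Working it through.** **Inputs.** Difference 0.7 days; SDs 2.65 and 2.51; two-sided 5%; 215 and 323 per arm; design effect (DE) 1.5 (all Protocol 9.1). Four schools, two per arm (SAP 3.3). Equal school sizes are my assumption.

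**Reproducing the plan.**
- Mean variance = (2.65² + 2.51²)/2 = (7.0225 + 6.3001)/2 = 6.661, so SD = 2.581.
- Normal approximation: n = 2 × 6.661 × (1.96 + 0.8416)²/0.7² = 213.4, rounded up to 214. The two-sample t calculation gives 215, which matches.
- 215 × 1.5 = 322.5, rounded up to 323. Then 323/0.7 = 461.4, rounded up to 462 per arm, or 924. Both match.

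**ICC implied by DE = 1.5.**
- Four schools: m = 646/4 = 161.5, so ICC = 0.5/160.5 = 0.0031.
- Three schools per arm: m = 107.7, so ICC = 0.0047.
- Four schools per arm: m = 80.75, so ICC = 0.0063.

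On the plan's own variance, an ICC of 0.0031 is a between-school SD of √(0.0031 × 6.661) = 0.14 ill days, about 2% of the assumed mean of 7.

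**Power with 323 completers per arm in two schools.** Effective n = 323/DE and δ = 0.7/√(2 × 6.661/effective n). The normal column is Φ(δ − 1.96). The last column is a noncentral t on 2 df (four school means less two arm means), with critical value 4.303. Every ICC other than 0.0031 is assumed.

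| ICC | DE | Effective n per arm | Power, normal | Power, 2 df |
|---|---|---|---|---|
| 0 | 1.00 | 323 | 93% | 47% |
| 0.0031 | 1.50 | 215.3 | 80% | 35% |
| 0.004 | 1.64 | 196.7 | 77% | 33% |
| 0.005 | 1.80 | 179.2 | 73% | 31% |
| 0.01 | 2.61 | 124.0 | 57% | 24% |
| 0.02 | 4.21 | 76.7 | 39% | 17% |

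**Limit with unlimited children.** As m grows, effective n per arm with two schools tends to 2/ICC. With normal critical values, 80% needs 215, so the ICC may not exceed 2/215 = 0.0093. With 2 df, 80% needs an effective n of about 869 per arm, so the ceiling is 2/869 = 0.0023. That is below the 0.0031 on which the plan relies.

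**The case against.** - **The arithmetic reproduces.** 215, 323 and 924 all come out. This stands: the fault is an unsupported planning assumption, not a miscalculation.
- **No document shows a larger ICC.** This also stands. Every value above 0.0031 is assumed, and just above it the loss is small; it becomes material from about 0.004. A reader might take the school eligibility rule, "No history of any outbreak or clustering of cases of infectious diseases in last month", as the sponsor's admission that illness is correlated within these schools. It is only an entry rule about the month before selection and says nothing about the correlation of nine-month totals.
- **There may be more than four schools.** The protocol sets a minimum, and three or four schools per arm would correspond to ICCs of 0.0047 or 0.0063. Those values would be equally undocumented, and the SAP fixes four schools.
- **Fewer dropouts would help.** With all 924 analysed (231 per school), normal-approximation power would be about 80% at ICC 0.005. The stated power, however, is for 646 completers.
- **Matching may reduce between-school variance.** It may, but neither the sample size calculation nor the SAP model uses the pairs.
- **The feasibility limit is disclosed.** Protocol 3.4 is open about it, but gives no figure for what it costs in power.

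**Conclusion.** The concern holds as an unjustified planning value. In the SAP's four schools, a design effect of 1.5 amounts to an ICC of 0.0031, which appears in neither document, and the 80% power is conditional on it. On the most generous calculation, power drops to 73% at an assumed ICC of 0.005 and 57% at 0.01. On the between-school degrees of freedom that go with the SAP's random-school model, it is about 35% at the plan's own implied ICC and does not reach 80% even at ICC 0. These figures assume four equal schools, 646 completers and the plan's means and SDs. The SAP names no degrees-of-freedom method; 2 df is what four school means in two arms leave.

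Two stronger readings should be resisted. One is that the true ICC is known to exceed 0.003; the documents give no estimate either way. The other is that the normal-approximation column, or the 0.0093 ceiling, is the trial's actual power or limit. It isolates the effect of the design effect, but it overstates power for a random-school analysis with two schools per arm.

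**What to change.** In Protocol 9.1 and SAP 1.4:

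1. State DE = 1 + (m − 1) × ICC with m = 161.5, and say that 1.5 corresponds to an ICC of about 0.003 with four equal schools. Give a justification for that value, or say that there is none.
2. Replace the single 80% figure with a power table over a stated range of assumed ICCs, computed with the degrees of freedom of the random-school analysis. With four schools and 2 df this gives about 47% at ICC 0, 35% at 0.0031, 31% at 0.005, 24% at 0.01 and 17% at 0.02. If a ceiling for 80% power is quoted, it should be about 0.0023.
3. Do not insert the normal-approximation powers or the 0.0093 ceiling as the trial's power.

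The ICC estimate already planned for SAP Table 14.2.2.2 should be kept, but an estimate from four schools is too imprecise to confirm or refute 0.003.

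The cost is revised wording in two sections and a less favourable stated power. No extra children are needed, and no endpoint or test changes.
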